#### **8.4.1. Time period and frequency for collecting AE, SAE, and other safety information**

All SAEs will be recorded and reported to the Sponsor or designee immediately and under no circumstance should this exceed 24 hours, as indicated in [Section 10.3](#). The Investigator will submit any updated SAE data to the Sponsor within 24 hours of it being available.

A poststudy AE/SAE is defined as any event that occurs outside of the AE/SAE reporting period.

Investigators are not obligated to actively seek information on AEs or SAEs after conclusion of the study participation. However, if the Investigator learns of any SAE, including a death, after a participant has been concluded from the study, the Investigator must record it in the medical records. If the Investigator considers the event to be reasonably related to the study intervention or study participation, the Investigator must promptly notify the Sponsor.

#### **8.4.2. Method of detecting AEs and SAEs**

Care will be taken not to introduce bias when detecting AEs and SAEs. Open-ended and nonleading questioning of the participant is the preferred method to inquire about AE occurrences.

#### **8.4.3. Follow-up of AEs and SAEs**

After the initial AE/SAE report, the Investigator is required to proactively follow each participant at subsequent visits/contacts. All SAEs (as defined in Section 8.4.3) will be followed until resolution, stabilization, the event is otherwise explained, or the participant is lost to follow-up (as defined in [Section 7.3](#)). Further information on follow-up procedures is provided in [Section 10.3.5.5](#).

#### **8.4.4. Regulatory reporting requirements for SAEs**

- Prompt notification by the Investigator to the Sponsor of an SAE is essential so that legal obligations and ethical responsibilities toward the safety of participants and the safety of a study intervention under clinical investigation are met. See [Section 8.4.4](#) for reporting timeframes.
- For SAE the Investigator must always provide an assessment of causality at the time of the initial report, as defined in the [Section 10.3.5.6](#).
- An Investigator who receives an Investigator safety report describing an SAE or other specific safety information (e.g., summary or listing of SAEs) from the Sponsor will review and then file it along with the (IB/ investigational directions for use [IDFU]/package insert or state other documents) and will notify the IRB/IEC, if appropriate according to local requirements.

**Table 6 Timeframes for submitting SAE, pregnancy and other events reports to GSK**

| Type of event | Initial reports |                             | Follow-up of relevant information on a previous report |                             |
|---------------|-----------------|-----------------------------|--|-----------------------------|
|               | Timeframe       | Documents                   | Timeframe  | Documents                   |
| SAEs          | 24 hours*‡      | electronic AEs Report       | 24 hours*  | electronic AEs Report       |
| Pregnancies   | 24 hours*       | electronic pregnancy report | 24 hours *   | electronic pregnancy report |

\* Timeframe allowed after receipt or awareness of the information by the Investigator/site staff.

‡ Paper AEs Report will be dated and signed by the Investigator (or designee). For each SAE, the Investigator must document in the medical notes that they have reviewed the SAE and have provided an assessment of causality.

#### 8.4.5. Pregnancy

Participant must be excluded from participation if the serum pregnancy result is positive.

- Details of all pregnancies in female participants and, if indicated, female partners of male participants will be collected after the start of study intervention and until time period for reporting pregnancies should align with the time period for postintervention contraception determined in [Section 5.1](#).
- If a pregnancy is reported, the Investigator will record pregnancy information on the appropriate form and submit it to the Sponsor within 24 hours of learning of the female participant or female partner of male participant (after obtaining the necessary signed informed consent from the female partner) pregnancy.
- Any pregnancy complication or elective termination of a pregnancy for medical reasons will be reported as an AE or SAE.
- Abnormal pregnancy outcomes (e.g., spontaneous abortion, foetal death, stillbirth, congenital anomalies, ectopic pregnancy) are considered SAEs and will be reported as such.
- The pregnant female partner will be followed to determine the outcome of the pregnancy. The Investigator will collect follow-up information on the pregnant female partner and the neonate and the information will be forwarded to the Sponsor.
- Any poststudy pregnancy-related SAE considered reasonably related to the study intervention by the Investigator will be reported to the Sponsor as described in [Section 8.4.5](#). While the Investigator is not obligated to actively seek this information in former study participants/pregnant female partner], he or she may learn of an SAE through spontaneous reporting.
- Any female participant who becomes pregnant while participating in the study will discontinue study intervention or be withdrawn from the study.

#### 8.4.6. Cardiovascular and death events

For any CV events detailed in [Section 10.3.3](#) and all deaths, whether or not they are considered SAEs, specific CV and Death sections of the eCRF will be required to be completed. These sections include questions regarding CV (including sudden cardiac death) and non-CV death.

The CV eCRFs are presented as queries in response to reporting of certain CV MedDRA terms. The CV information should be recorded in the specific CV section of the eCRF within one week of receipt of a CV Event data query prompting its completion.

The Death eCRF is provided immediately after the occurrence or outcome of death is reported. Initial and follow-up reports regarding death must be completed within one week of when the death is reported.

#### **8.4.7. Disease-related events and/or disease-related outcomes not qualifying as AEs or SAEs**

Not applicable as this is a healthy volunteer study.

#### **8.4.9. Participant Card**

The Investigator (or designee) must provide the participant with a “participant card” containing information about the clinical study. The participants must be instructed to always keep the participant card in their possession for the duration of the study. In an emergency, this card serves to inform the responsible attending physician that the participant is in a clinical study and that relevant information may be obtained by contacting the Investigator or their back up.

### **8.5. Pharmacokinetics**

Blood samples will be collected for measurement of plasma concentrations of study intervention as specified in the SoA (Section 1.3). Blood sample collection, processing and shipping details will be outlined in a separate laboratory manual.

Instructions for the collection and handling of biological samples will be provided by the Sponsor. The actual date and time (24-hour clock time) of each sample will be recorded.

## **8.6. Pharmacodynamics**

Pharmacodynamics (other than cardiac effects as described elsewhere) are not measured in this study.

## **8.7. Genetics**

Genetics are not evaluated in this study.

## **8.8. Biomarkers**

Biomarkers are not evaluated in this study.

## **8.9. Immunogenicity assessments**

Immunogenicity is not assessed in this study.

## **8.10. Health economics or medical resource utilization and health economics**

Health economics OR Medical resource utilization and health economics parameters are not evaluated in this study.

# **9. STATISTICAL CONSIDERATIONS**

The SAP will be finalized prior to database lock and it will include a more technical and detailed description of the statistical analyses described in this section. This section is a summary of the planned statistical analyses of the most important endpoints including primary and key secondary endpoints.

## **9.1. Statistical hypothesis/hypotheses/comparisons**

### **9.1.1. Multiplicity Adjustment**

No multiplicity adjustment will be required to test hypotheses endpoints.

## 9.2. Analysis sets

| Analysis Set   | Definition / Criteria   | Analyses Evaluated   |
|----------------|---|--|
| Screened       | 
 
All participants who were screened for eligibility.
 
   | 
 
Study Population
 
 |
| Enrolled       | 
 
All participants who entered the study (who received study intervention)
 
Note screening failures (who never passed screening even if rescreened) and participants screened but never enrolled into the study (Met eligibility but not needed) are excluded from the Enrolled analysis set as they did not enter the study.
 
 | 
 
Study Population
 
 |
| PK             | 
 
All participants in the Safety analysis set who had at least 1 non-missing PK assessment (non-quantifiable values will be considered as non-missing values).
 
Data will be reported according to the actual study intervention.
 
   | 
 
Primary analysis
 
 |
| PD             | 
 
All participants in the Safety analysis set who had at least 1 non-missing ECG assessment.
 
Data will be reported according to the actual study intervention.
 
   | 
 
Primary analysis
 
 |
| Safety/Exposed | 
 
All participants who received at least one dose of study intervention.
 
Data will be reported according to the actual study intervention.
 
   | 
 
Safety
 
           |

## 9.3. Statistical analyses

### 9.3.1. General considerations/definitions

All data will be listed and descriptive analysis along with appropriate graphs will be provided. Categorical data shall be summarized by means of absolute and relative frequencies (counts and percentages) and continuous data by means of the number of observations, the arithmetic mean, standard deviation, minimum, median, maximum, CI, geometric mean and coefficient of variation as appropriate.

### 9.3.2. Primary endpoint analysis

#### 9.3.2.1. Definition of endpoints

The primary endpoint is Change from baseline in QTc ( $\Delta QTc$ ) where baseline is the pre dose collection at Visit 2.

#### 9.3.2.2. Main Analytical Approach

A random-coefficient mixed-effects model will be fit to all available paroxetine concentration -  $\Delta QTc$  data pairs, as described in a white paper ([Garnet, 2017](#)). In this model,  $\Delta QTc$  is the dependent variable and paroxetine concentration and time after dose are independent variables, it takes the form of:

$$\Delta QTc_{i,k} = (\theta_0 + \eta_{0,i}) + (\theta_1 + \eta_{1,i}) * C_{i,k} + \theta_2 * TIME_{i,k} + \theta_3(QTc_{i,k=0} - \overline{QTc_0}) + \varepsilon_{i,k}$$

In this equation  $\Delta QTc_{i,k}$  is the change from baseline in QTc for subject i at time k;  $\theta_0$  is the population mean intercept in the absence of a treatment effect;  $\eta_{0,i}$  is the random effect associated with the intercept term  $\theta_0$ ;  $\theta_1$  is the population mean slope of the assumed linear association between concentration and  $\Delta QTc_{i,k}$ ;  $\eta_{1,i}$  is the random effect associated with the slope  $\theta_1$ ;  $C_{i,k}$  is the concentration for participant i and time k;  $\theta_2$  is the fixed effect associated with time; and  $\theta_3$  is the fixed effect associated with the difference of each baseline values to the overall mean ( Baseline  $QTc_{i,k=0}$ ,  $QTc_0$  is overall mean of  $QTc_{i,k=0}$ , i.e., the mean of all the baseline (= time 0) QTc values). It is assumed the random effects are normally distributed with mean [0,0] and an unstructured covariance matrix G, whereas the residuals are normally distributed with mean 0 and variance R. The  $\Delta QTc$  and paroxetine concentrations corresponding to all doses (20, 40, and 60mg) will be used for the modelling (both drawn from each participant at same time intervals). This model includes a linear correlation between paroxetine plasma concentration and  $\Delta QTc$ .

This model will be estimated including the precision around the parameter estimates. The geometric mean of the individual  $C_{max}$  values for participants at the 60 mg dose will be calculated. Based on the estimated model, and the calculated geometric mean  $C_{max}$  for dose 60 will be used in the fitted model to predict the upper limit of the 90% CI of  $\Delta QTc$  at dose 60 mg

The summary measure of the study is the geometric mean and 90% CI of the predicted  $\Delta QTc$  at  $C_{max}$ . If the upper bound of 90% CI for the geometric mean of QTc corresponding to the  $C_{max}$  of paroxetine concentration at dose 60mg of that prediction falls below the 10 msec mark, the conclusion of the study is that there is no clinically relevant QTc prolongation up to and including the 60 mg dose. In case the upper 90% CI limit does not fall below the 10 msec mark, the same evaluation will be performed for the  $\Delta QTc$  at the geometric mean  $C_{max}$  of the 40 mg once daily dose. Intercurrent events and handling of missing data:

1. The data will be affected by occurrence of the intercurrent event (Treatment discontinuation of the study) would be treated as missing at random from the

occurrence of the intercurrent event until the end of the study. Participant level missing data considered as missing at random, will not be imputed and available data will be used in the primary analysis.

2. The treatment policy strategy for events affecting absorption within 1 hour is used for the estimation model as it is based on concentration not dose - therefore even though the concentration may be affected, the data is still relevant for quantifying the relationship between change in QTc and drug concentration. Hence, we will use all the data in the modelling (paroxetine concentration and  $\Delta$ QTc) irrespective of the occurrence of the intercurrent event. However, when the model is used to predict the upper 90% CI for 60mg doses an absorption event may artificially reduce the prediction, hence the corresponding paroxetine concentration data will not be used in the calculation of the  $C_{max}$  at and in the prediction of the geometric mean of predicted  $\Delta$ QTc and 90% CI.

Detailed analysis will be described in Statistical Analysis Plan.

### **9.3.2.3. Sensitivity Analyses**

In case 20% or more (8 participants or more) participants at the 60 mg once daily dose have either missing paroxetine concentration data around the  $C_{max}$  at the 60 mg dose level, or an intercurrent event of “any events affecting absorption within 1 hour of the dose” at the 60 mg dose, a sensitivity analysis will be performed to ensure that there is no bias in the calculated geometric mean of the  $C_{max}$  at the 60 mg once daily dose. This analysis will consist of pharmacokinetic model-fitting of the individual paroxetine concentration data without the estimation of population level parameters (post-hoc or Bayesian fit). This will allow the prediction of the  $C_{max}$  at the 60 mg once daily dose for those participants with missing data, based on the available paroxetine concentration data at the earlier doses. Through this method, a geometric mean of  $C_{max}$  at the 60 mg dose can be calculated that should be less affected by dropout, missing data, or intercurrent events. An additional calculation of the upper limit of the 90% CI of  $\Delta$ QTc will then be performed using the  $C_{max}$  of the 60 mg dose calculated using this method. In case the evaluation of  $\Delta$ QTc finds a  $\geq 10$  ms upper 90% CI limit at the 60 mg dose, the same model-based prediction of  $C_{max}$  at the 40 mg dose for dropouts will be performed, where required. Details of this analysis will be described in the Statistical Analysis Plan.

### **9.3.3. Secondary endpoint(s)/estimand(s) analyses**

- The summary of the absolute value and its change from baseline in each vital sign parameter will be provided across the entire intervention. Frequency counts and percentages will be provided for abnormalities.
- Frequency counts and percentages will be provided for all the reported Adverse Events (AEs) and Serious Adverse Events (SAEs).

### 9.3.3.1. Safety analysis

Safety parameters such as occurrence of Adverse events (AEs) and Serious adverse events (SAEs), clinically significant changes in physical examination findings, vital signs, and ECG will be descriptively summarized as appropriate. The change from baseline for, vital signs, and ECG will be reported across the intervention period. All safety analyses will be performed on the safety population.

## 9.4. Interim analyses

No interim analysis is planned for this study.

## 9.5. Sample size determination

At least 36 participants, men or non-pregnant women, aged 18 to 65 years will be enrolled. This number is expected to result in sufficiently wide range of paroxetine concentrations to cover those typically observed in a real-world clinical setting. A Monte Carlo simulation analysis was used to determine the probability of the 90% upper limit of the CI of the  $\Delta$ QTc at the geometric mean of the 60 mg dose encompassing the 10 ms cut-off value. Based on this simulation approach, it is expected that under the assumption of no true effect of paroxetine on QTc at the 60 mg dose, the expected probability of incorrectly detecting an effect (90% upper limit of the CI  $\geq$ 10 ms) is <1% (false positive) when inclusion is 36 participants. In case the true effect is 5 ms, the expected probability of a false positive is <2%. When the true effect is 10 ms, the expected probability of correctly determining a QTc prolongating effect is approximately 82%.

The sensitivity of missing data was also assessed. With 20% drop out at the 40 mg dose and another 25% drop out at the 60 mg dose (in addition to the drop out at the 40 mg dose) the expected probability of incorrectly detecting an effect (90% upper limit of the CI 10 msec) for 36 participants is 1% (false positive) when the true effect is null. The expected probability of a false positive is 5% if the true effect is 5 msec. The expected probability of correctly determining a QTc prolonging effect is approximately 85% when the true effect is 10 msec.

Please refer [Appendix 2 \(sample size determination section\)](#) for further details.

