### **Number of Participants:**

The number of participants was selected based on the required variability in paroxetine concentrations to assess the cardiac effects. At least 36 participants and no more than 40 healthy participants, men or non-pregnant women, aged 18 to 65 years will be enrolled. This number, in combination with the 3 dose titration steps, is expected to result in a sufficiently wide range of paroxetine concentrations to cover those typically observed in a real-world clinical setting.

In addition, a previous pharmacokinetics (PK) drug-drug interaction study of paroxetine and pimozide in 40 healthy subjects used a dose titration up to 60 mg once daily in intervals of 20 mg per 5 days (GSK document HM2004/00372/01). Of these 40 subjects, 33 subjects had evaluable QTc data at the 60 mg dose. Although 11 subjects dropped out in total by the end of the study, approximately half of those dropouts were in relation to the combination of the two investigated compounds which were found to interact. This study showed that the 60 mg once daily dose can be achieved, at the expected rate of titration, without prohibitive dropout rates. The current titration schedule increases the time stayed at the same dose to 7 days to improve participant retention.

A Monte Carlo simulation analysis was used to determine the probability of the 90% upper limit of the CI of the  $\Delta$ QTc at the geometric mean of the 60 mg dose encompassing the 10 msec cut-off value. Based on this simulation approach, it is expected that under the assumption of no true effect of paroxetine on QTc at the 60 mg dose, the expected probability of incorrectly detecting an effect (90% upper limit of the CI  $\geq$  10 msec) is <1% (false positive) with the inclusion of 36 participants. In case the true effect is 5 msec, the expected probability of a false positive is <2%. When the true effect

is 10 msec, the expected probability of correctly determining a QTc prolongating effect is approximately 82%. For further details, see Section 9.5.

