The sensitivity of missing data was also assessed. With 20% drop out at the 40 mg dose and another 25% drop out at the 60 mg dose (in addition to the drop out at the 40 mg dose) the expected probability of incorrectly detecting an effect (90% upper limit of the CI 10 msec) for 36 participants is 1% (false positive) when the true effect is null. The expected probability of a false positive is 5% if the true effect is 5 msec. The expected probability of correctly determining a QTc prolonging effect is approximately 85% when the true effect is 10 msec.

**Note:** "Enrolled" means a participant, agrees to participate in a clinical study following completion of the informed consent process. Potential participants who are screened for the purpose of determining eligibility for the study, but do not participate in the study, are not considered enrolled, unless otherwise specified by the protocol.

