**Table 10      Sample Size Sensitivity without dropout**

| True effect | 0 msec  | 5 msec | 10 msec |
|-------------|---|--------|---------|
| N    | Probability of the upper 90% limit of model-predicted <math>\Delta</math>QTc being <math>\geq 10</math> msec |        |         |
| 20   | 0   | 4.3    | 80.3    |
| 30   | 0   | 1.8    | 82.8    |
| 36   | 0   | 0.6    | 82.5    |
| 46   | 0   | 0.4    | 84.2    |
| 56   | 0   | 0.1    | 85.3    |

The sensitivity of the probability of correctly determining a QTc prolonging effect is calculated with respect to different sample sizes (20, 30, 36, 46, 56) and assuming true effect as 0 msec, 5 msec, and 10 msec. Additionally, it incorporates a 20% drop out at the 40 mg dose and another 25% drop out at the 60 mg dose (in addition to the drop out at the 40mg dose).

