The  $\Delta QTc$  and paroxetine concentrations corresponding to all doses (20, 40, and 60mg) will be used for the modelling (Both drawn from each participant at same time intervals). Moreover,  $\Delta QTc$  obtained on Visit 2 (Day -1) after baseline will be included in the model with paroxetine concentrations set to 0. This model assumes a linear correlation between paroxetine plasma concentration and  $\Delta QTc$ . While it is assumed that such a correlation (if at all) can be considered linear at clinically meaningful doses, other parameterizations such as the classical Emax function may be explored if the linear approach is found inappropriate.

The model parameters will be estimated including the precision around the parameter estimates using a maximum likelihood approach.

The following SAS® code will be used for the random-coefficient linear mixed-effects model:

```
PROC MIXED DATA=ADEG (WHERE=(XXXX)) NOITPRINT CL NOCLPRINT METHOD=ML PLOTS=NONE;
ODS OUTPUT SOLUTIONF=SOLF ESTIMATES=ESTF COVPARMS=COV;
CLASS USUBJID ATPTN ;
MODEL CHG=BASEC ATPTN PCSTRESN / DDFM=KR SOLUTION ALPHAP=.05 CL RESIDUAL
OUTPM=PRED OUTP=IPRED;
RANDOM INT PCSTRESN /SUB=USUBJID TYPE=UN;
ESTIMATE "DDQTC_60MG" INT 1 PCSTRESN CMAX60MG /CL ALPHA=.1;
RUN;
```

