#### 4.9.2.3 Summary of measure

Individual Cmax values for participants at the 60 mg dose will be used to calculate the Cmax geometric mean. Based on the estimated model, the calculated geometric mean Cmax for dose 60 mg will be used in the fitted model to predict the upper limit of the 90% CI of  $\Delta QTc$  at dose 60 mg as follows (in the case of a linear model):

$$\overline{\Delta QTc_{60mg}} = \theta_0 + \theta_1 Cmax(60mg)$$

$$90\% CI = \overline{\Delta QTc_{60mg}} \pm t(0.95, DF) \times SE$$

$$SE = \sqrt{var(\theta_0) + C_{max}^2(60 mg) var(\theta_1) + 2C_{max}(60 mg) \times cov(\theta_0, \theta_1)}$$

Where:

- $\overline{\Delta QTc_{60mg}}$  is the predicted  $\Delta QTc$  at 60 mg;
- $\theta_0$  is the estimated fixed intercept term;
- $\theta_1$  is the estimated fixed slope for concentrations;
- $t(0.95, DF)$  is the 95th quantile from the student distribution with  $DF$  degrees of freedom;
- SE is the standard error ;
- $var(\theta_0)$ ,  $var(\theta_1)$  and  $cov(\theta_0, \theta_1)$  are respectively the variance of  $\theta_0$  and  $\theta_1$  and their covariance.

The summary measure of the study is the geometric mean and 90% CI of the predicted  $\Delta QTc$  at 60 mg Cmax. If the upper bound of 90% CI for this predicted  $\Delta QTc$  falls below the 10 msec mark, the conclusion of the study is that there is no clinically relevant QTc prolongation up to and including the 60 mg dose. In case the upper 90% CI limit does not fall below the 10 msec mark, the same evaluation will be performed for the  $\Delta QTc$  at the geometric mean Cmax of the 40 mg once daily dose.

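### At a true effect of 10 msec the stated 82% (85% with dropout) does not match the nominal 95% of the planned interval with Cmax fixed, and the simulation inputs that could explain the gap are not given

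*Protocol*

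**What the plan says.** Protocol 9.5 gives the result of a Monte Carlo simulation at N=36: "When the true effect is 10 ms, the expected probability of correctly determining a QTc prolongating effect is approximately 82" percent. The Synopsis (Protocol 1.1, Number of Participants) gives the same figure. For the dropout scenario both say: "The expected probability of correctly determining a QTc prolonging effect is approximately 85% when the true effect is 10 msec". SAP 4.16 repeats both figures. Protocol Appendix 2 (Tables 10 and 11) and the matching SAP tables give the grid behind them, headed "Probability of the upper 90% limit of model-predicted" ΔQTc being at least 10 msec.

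The analysis is set out in SAP 4.9.2 and 4.9.2.3. The upper limit is the estimate plus t(0.95, DF) times the SE. The SAS statement is "PCSTRESN CMAX60MG /CL ALPHA=.1", so the interval is a two-sided 90% CI and Cmax enters as a constant. The SE contains only the variances of intercept and slope and their covariance. The Cmax itself comes from the trial's own data: "Individual Cmax values for participants at the 60 mg dose will be used to calculate the Cmax geometric mean". If the upper limit "falls below the 10 msec mark, the conclusion of the study is that there is no clinically relevant QTc prolongation" up to and including 60 mg.

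Protocol 9.5 sends the reader to Appendix 2 for details. Appendix 2 holds only the sample sizes, true effects, dropout rates and results. The variances, PK inputs, Cmax handling, true-effect definition, interval construction and number of replicates are not stated.

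**The concern.** When the true effect equals the threshold, the chance that the upper limit reaches the threshold is the one-sided coverage of the interval. It is set by the confidence level and hardly depends on N. A two-sided 90% CI should give 95%, but the plan reports 80–86% in every cell. It describes this as the chance of correctly determining an effect, which reads like power.

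The whole conclusion rests on this one limit, and the 10 msec column is the only stated figure that bears on false reassurance at the threshold. Either it does not describe the planned analysis, or it shows that the planned interval is too narrow for a population target. The sponsor should know which before database lock.

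**Working it through.** **1. The plan's own figures** (Protocol Tables 10 and 11; SAP 4.16), 10 msec column, in percent:

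| N | No dropout | With dropout |
|---|---|---|
| 20 | 80.3 | 80.5 |
| 30 | 82.8 | 83.3 |
| 36 | 82.5 | 85.1 |
| 46 | 84.2 | 86.1 |
| 56 | 85.3 | 84 |

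The prose figures (82% and 85%) agree with the N=36 row. The mean of the ten cells is 83.4%.

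**2. Benchmark.** Let U = estimate + q × SE. If the true value is 10 msec at a fixed Cmax and the SE is right, P(U ≥ 10) = Φ(q), whatever the N or the variances.
- Two-sided 90% CI: Φ(1.645) = 95.0%.
- One-sided 90% limit: Φ(1.282) = 90.0%.
- Two-sided 95% CI: Φ(1.960) = 97.5%.

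Finite-sample estimation does not change this much. Maximum-likelihood fits of the SAP model were simulated at N=36, with 800 runs in each of eight settings. The assumed inputs were slope SD/residual SD of 3/5 or 6/6 msec and Cmax log-SD of 0.3 to 0.9. Evaluated at a fixed Cmax, they gave 93.1–95.8%.

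**3. Gap at N=36.** 95.0 − 82.5 = 12.5 points without dropout and 95.0 − 85.1 = 9.9 points with it. The ten cells imply q between Φ⁻¹(0.803) = 0.85 and Φ⁻¹(0.861) = 1.08, against the planned 1.645.

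**4. Simulation noise.** The replicate count is not stated. If all cells share one count, the smallest that reproduces all 30 table entries is 800. The Monte Carlo SE at 95% is then √(0.95 × 0.05/800) = 0.0077, and the closest cell (86.1%) lies 0.089/0.0077 = 11.6 SE low. If each row is allowed its own smallest possible count (81 to 667), the closest cell is 84.0% at 81 replicates, and 0.110/0.0242 = 4.5 SE low. Against 90%, two single cells are then only 1.5 and 1.8 SE low, but the ten pooled (83.8% of 2249) are 9.9 SE low.

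**5. Could an estimated Cmax explain it?** Let s be the log-SD of Cmax and n60 the number of participants at 60 mg. This is N without dropout and 0.8 × 0.75 × N = 0.6N with it. If each run is evaluated at its own geometric mean Cmax while the target is the population value, then approximately SD² = SE² + effect² × s²/n60. The 5 and 10 msec cells give two equations:
- q × SE/SD₁₀ = z₁₀
- (q × SE − 5)/SD₅ = z₅

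N=36 without dropout, two-sided limit: z₁₀ = Φ⁻¹(0.825) = 0.935 and z₅ = Φ⁻¹(0.006) = −2.51. The solution is SE = 1.05 and SD₁₀ = 1.645 × 1.05/0.935 = 1.85. Hence s²/36 = (1.85² − 1.05²)/100 ≈ 0.0233, s ≈ 0.92, and CV = √(exp(s²) − 1) ≈ 115%.

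Over all ten rows:
- two-sided 90% limit: s 0.79–0.95, CV 94–122%
- one-sided 90% limit: s 0.52–0.78, CV 56–92%

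The direct fits of step 2, evaluated instead at the sample geometric mean Cmax, move the same way. For log-SD 0.3, 0.5, 0.7 and 0.9 they give 93.5, 89.5, 85.5 and 83.1% (3/5 setting) and 94.9, 91.5, 89.5 and 86.5% (6/6 setting).

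**6. Could an offset in the true effect alone explain it?** Take SE proportional to 1/√N (an assumption) and anchor at N=36: offset/SE = 1.645 − 0.935 = 0.710. At N=20 it is 0.710 × √(20/36) = 0.529, giving Φ(1.116) = 86.8%. At N=56 it is 0.710 × √(56/36) = 0.886, giving Φ(0.759) = 77.6%. The column would fall with N, whereas the stated one rises from 80.3% to 85.3%. An offset alone does not fit.

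**The case against.** The best reply is that no passage promises 95%. That benchmark holds only with Cmax fixed, and the plan recalculates the geometric mean Cmax from its own participants. A simulation that followed the plan would do the same in every run and could land in the low 80s. The figures also come from the protocol, whose model has a single time coefficient and names no t quantile, so they need not match the later SAP model. The estimand does not say whether its Cmax is the population or the observed value. If it is the observed value, the planned interval is nominally correct.

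Much of this stands. A reader might infer that 82% is a miscalculation; the documents do not show that, because an estimated Cmax could produce it. A reader might also infer that the Cmax CV must be near 100% or more. That is not required: a one-sided limit needs only 56–92%, and a two-sided limit with a −0.5 msec offset fits with 50–102%. Protocol 2.2 cuts both ways, since it describes saturable, polymorphic metabolism but also says that between-subject variability shrinks with dose and duration. Finally, a reader might infer that the trial is underpowered. The Synopsis does not rest N on this figure: "The number of participants was selected based on the required variability in paroxetine concentrations to assess the cardiac effects".

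The reply does not remove the problem. The value Φ(q) does not depend on how time is modelled. If the target is the observed or a fixed Cmax, 82% and 85% do not describe the planned interval. If the target is the population Cmax, the planned SE omits a real source of variance and the interval under-covers. Something needs correcting on either reading.

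**Conclusion.** The mismatch is established: 80.3–86.1% in ten cells, against a nominal 95% for the planned two-sided interval with Cmax fixed, or 90% for a one-sided 90% limit. Noise does not account for it.

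The cause is not established. An estimated Cmax is a coherent candidate, but it rests on the approximation in step 5 and on a Cmax CV that the documents do not give. An interval built differently, or a mix of causes, remains possible.

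The risk of wrongly concluding no prolongation at a true 10 msec therefore lies somewhere between about 5% and, at N=36, 100 − 82.5 = 17.5% (100 − 85.1 = 14.9% with dropout). A reader might take 17.5% as the trial's actual risk. That follows only if the simulation used the planned interval and a population target, which is not stated. The 0 and 5 msec columns have not been shown to be wrong.

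This should be fixed. It does not call the sample size into question.

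**What to change.** 1. State whether the target is the effect at the population or the observed 60 mg geometric mean Cmax. Re-run the simulation with the SAP 4.9.2 model and interval, evaluating each run at its own sample geometric mean Cmax.
2. Replace all three columns (0, 5 and 10 msec) of both tables, and the matching prose in Protocol 1.1, 9.5 and Appendix 2 and in SAP 4.16. Changing only the 10 msec column would mix two simulations in one table. Name the limit as the upper limit of the two-sided 90% CI, and state the true-effect definition, variance and PK inputs, Cmax handling and number of replicates.
3. Reword the 10 msec sentence, for example: *At a true effect of 10 msec at the 60 mg geometric mean Cmax, the upper limit of the two-sided 90% CI is at least 10 msec in X% of simulations (nominal 95% with Cmax fixed); the risk of wrongly concluding no prolongation is (100 − X)%.*
4. If the target is the population Cmax and the re-run shows under-coverage, add a pre-specified sensitivity CI that carries the Cmax uncertainty. It could be a participant-level bootstrap that refits the model and recomputes the geometric mean Cmax, or the added variance term θ₁² × Cmax² × Var(mean log Cmax).

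The cost is one simulation re-run, text edits in two documents, and possibly a slightly wider sensitivity CI. Sample size, primary interval and decision rule stay as written.
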